#### **14.3.2 Analysis of Secondary Efficacy Endpoints**

The following binary efficacy endpoints will be analyzed using a Cochran-Mantel-Haenszel test adjusted for dosing regimen based on OC and imputation with missing efficacy response considered as the non-responder (i.e., IGA success) and missing relapse response considered as a relapse (i.e., increase in PP NRS or IGA):

- Proportion of subjects with increase in PP NRS score  $\geq 2$  points from baseline at each scheduled visit
- Proportion of subjects maintaining IGA success, defined as IGA score of 0 (clear) or 1 (almost clear) at each scheduled visit
- Proportion of subjects with increase in IGA  $\geq 2$  points from baseline at each scheduled visit

The estimate of treatment difference (nemolizumab minus placebo), the corresponding 2-sided 95% CI, and p-values will be presented.

The following continuous efficacy endpoints will be analyzed using analysis of covariance (ANCOVA) based on OC with treatment group and dose regimen as factors, and baseline value as the covariate. They will also be analyzed using the mixed effect model for repeated measure (MMRM) approach, including treatment group and dose regimen as factors, visit, interaction term between treatment and visit, and the corresponding baseline value as independent covariate.

- Absolute and percent change from baseline in PP NRS at each scheduled visit
- Absolute and percent change from baseline in SD NRS at each scheduled visit
- Change from baseline in DLQI at Week 16 and Week 24

The multiple imputation methods may be used as sensitivity analysis for some selected secondary efficacy endpoints.

#### **14.4 Safety Analysis**

##### **Extent of Exposure**

The duration of exposure will be summarized by treatment and dosing regimen. The number of subjects exposed to study medication will be summarized by visit, treatment group, and dosing regimen.

## **Adverse Events**

All reported AEs will be coded using the most recent version of Medical Dictionary for Regulatory Activities (MedDRA). Treatment-emergent AEs, defined as those AEs occurring after the first administration of study treatment until the end of the follow-up period, will be tabulated in frequency tables by system organ class and preferred term. These TEAEs may also be reported separately for treatment period and follow-up period. Additional summary tables will be provided for SAEs, treatment-related AEs (reasonable possibility, no reasonable possibility), AESIs, and AEs leading to treatment discontinuation. For a given AE, a subject will be counted once even if he/she has experienced multiple episodes of that particular AE.

## **Clinical Laboratory**

Laboratory data (absolute values and change from baseline) will be summarized by visit, treatment group and dosing regimen. In addition, the number and percentage of subjects below, within, and above the laboratory reference ranges, and the number and percentage of subjects who met criteria of potential clinically significant value will be summarized by visit, treatment group, and dosing regimen. Shift tables will be generated using the reference ranges. Reference ranges will be provided in the laboratory manual.

## **Vital Signs**

All vital signs (absolute values and change from baseline) will be summarized by visit, treatment group, and dose regimen. In addition, the number and percent of subjects with clinically significant abnormal values (of clinical concern as identified by the Investigator) will be summarized by visit, treatment group, and dosing regimen.

## **12-Lead ECG**

The number and percentage of subjects who have ECGs that are abnormal/clinically significant and abnormal/not clinically significant will be displayed by visit, treatment, and dosing regimen.

## **Respiratory Assessments**

The results (absolute values and change from baseline) of PEF testing and respiratory examination will be summarized by visit, treatment group, and dose regimen. ACT for subjects with a medical history of asthma or newly-diagnosed asthma will be listed.

## **Concomitant Therapies and Procedures**

Concomitant therapies will be coded according to the most recent version of the World Health Organization (WHO) Drug Dictionary Enhanced for Concomitant Medication. Concomitant therapies and procedures will be summarized.

Summary tables will be provided for concomitant medications initiated during the study period.

## 14.5 Proof of Exposure and Anti-Drug Antibody Analysis

The nemolizumab serum concentration and ADA will be summarized by visit in the POE analysis population.

For serum concentrations (POE), descriptive statistics will include arithmetic and geometric mean, standard deviation, coefficient of variation [%CV], median, minimum, maximum. A 95% confidence interval [CI] of mean and number of Below Limit of Quantifications will be presented. Any potential exposure-safety relationship will also be explored. Below Limit of Quantifications will be considered as missing and excluded from the descriptive summary.

For ADA analyses, the incidence of positive ADA results will be summarized (absolute occurrence, percent of subjects, and treatment-related ADA). A presentation of ADA results will be detailed in the SAP.

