Safety:	
The following safety assessments are planned according to the Schedule of Assessments (Table 7):
 
 
• AEs, including TEAEs, AESIs, SAEs, treatment-related AEs, and AEs leading to discontinuation
 
• Physical examination and vital signs
 
• Clinical laboratory tests
 
• 12-lead ECGs
 
• Respiratory examination and assessments
 

Proof of Exposure/ Immunogenicity :	
Proof of exposure (POE) and immunogenicity assessments are planned according to the Schedule of Assessments (Table 7):
 
 
• Serum nemolizumab concentrations for POE
 
• Anti-drug antibody (ADA) assessments: screening, confirmatory, titer, and neutralizing antibody (Nab) assays
 

Statistical Methods and Planned Analyses:	
The ITT population will consist of all randomized subjects. The safety population will include all randomized subjects who receive at least 1 dose of study drug. The POE analysis population will include all subjects in the safety population who provide at least 1 post-baseline evaluable drug concentration value. The per-protocol population will consist of all subjects in the ITT population who have no major protocol deviations that would have a significant effect on the efficacy of the study treatment. The ITT population will be the primary population for all efficacy analyses, and all safety data will be summarized based on the safety population. The per-protocol population will be used as the population for sensitivity analyses of the primary and key secondary efficacy endpoints.
 
Primary Efficacy Endpoints:
 
Median time to relapse, 25th and 75th percentiles, and 95% confidence interval (CI) will be presented. Kaplan-Meier survival plots will be produced. Time to relapse from baseline will be analyzed using Cox proportional hazards model adjusted for dosing regimens, comparing the

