#### Proof of Exposure Analysis Population

The POE analysis population will include all subjects in the safety population who provide at least 1 measurable post-baseline evaluable drug concentration value.

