10.2.4. Dermatology Life Quality Index

The DLQI is a validated 10-item questionnaire covering domains including symptoms/feelings, daily activities, leisure, work/school, personal relationships, and treatment.

The subject will rate each question ranging from 0 (not at all) to 3 (very much). The DLQI total score is calculated by summing each questionnaire. Total score will have a maximum score of 30 and a minimum of 0. The higher score indicated a poorer quality of life.

DLQI will be collected at Baseline, Week 16, Week 24 and Early Termination. DLQI total score will be summarized as a continuous variable using OC on the ITT Population. Absolute change and percentage change from Baseline in DLQI total score will also be summarized.

Absolute change from Baseline in DLQI will be analyzed using ANCOVA based on OC, including treatment group dose regimen as factors with baseline value as covariate. The least squares means (LSMeans), standard error of LSMeans, and 95% CI for change from baseline, as well as the difference in LSMeans between the treatment groups, the two-sided 95% CI, and associated p-value will be presented. Percentage change from Baseline in DLQI will not be analyzed because of the small sample size and potential high skewness of the data.

This document is confidential.

11. Pharmacokinetics

The serum concentration of Nemolizumab will be assessed at Baseline, Week 24 and Early Termination visit. PK analyses are required during any unscheduled visit conducted for safety reasons. As a guideline, PK samples should be collected at approximately the same time of day throughout the study, to the extent possible, before study drug injection (pre-dose samples).

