11.1. Pharmacokinetic Concentration Presentation

Serum concentration data (unit: ng/mL) will be summarized on the POE analysis population by visit and by dosing regimen from Baseline and Week 24, using the following statistics: arithmetic mean, SD, coefficient of variation (CV), geometric mean, geometric CV, median, minimum, maximum, 95% CI of the arithmetic mean, and number below the limit of quantification (BLQ).

Mean and individual (spaghetti plot) serum concentration(s) will be plotted by visit and by dosing regimen on both a linear and semi-logarithmic scale on the POE analysis population (2 plots).

Individual serum concentrations will be listed on the POE analysis population.

This document is confidential.

12. Immunogenicity

Blood samples to assess anti-Nemolizumab ADA will be collected at Baseline, Week 24 and Early Termination. Immunogenicity analyses will be summarized on the POE analysis population.

Details related to the processing of serum samples and the assessments of ADA will be described in the bioanalytical plan, which will be finalized before the beginning of sample analysis. Results will be described in the bioanalytical report, which will be included as an appendix in the final clinical study report.

Incidence of positive ADA results will be summarized (absolute occurrence and percent of subjects) and plotted by dosing regimen at each visit. The concentration of ADA titer (ng/mL) and neutralizing antibodies (ng/mL) will be summarized as continuous variables.

The number and percentage of subjects with treatment related ADA will be summarized by visit and dosing regimen. A treatment-related ADA is defined when the Baseline or confirmatory ADA result is negative and the post-baseline confirmatory ADA result is positive in the Nemolizumab treated group only.

Individual trough serum drug concentrations will be plotted over time in ADA-positive versus ADA-negative subjects.

This document is confidential.

13. Safety

All safety data will be summarized and listed on the SAF population.

Safety assessments will be conducted for all subjects at the baseline visit and at every subsequent visit. Safety will be assessed on the basis of AEs (including TEAEs, AESIs, and SAEs), physical examination and vital signs, clinical laboratory tests, electrocardiogram (ECG) and respiratory assessments. Summary of all safety endpoints will be presented for each treatment group.

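### The proof-of-exposure population requires a measurable post-baseline level, so a nemolizumab-treated subject below the assay limit at the one scheduled post-baseline sample drops out of the exposure and ADA summaries

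*Protocol*

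**What the plan says.** - **Population.** Protocol 14.2 takes safety-population subjects who "provide at least 1 measurable post-baseline evaluable drug concentration value". SAP 6.3 uses the same criterion. The protocol synopsis (Statistical Methods) takes those "who provide at least 1 post-baseline evaluable drug concentration value", without *measurable*. Protocol 14 lets the SAP prevail where the two differ. Neither document defines *measurable*.
- **Sampling.** SAP 11: "The serum concentration of Nemolizumab will be assessed at Baseline, Week 24 and Early Termination visit". Further samples are taken only at unscheduled visits, mainly those made for safety. Protocol 9.3.2 restricts the assay to samples from nemolizumab-treated subjects. Protocol 13.1.2 gives the LLOQ as 100 ng/mL.
- **Below-limit values.** Protocol 14.5: "Below Limit of Quantifications will be considered as missing and excluded from the descriptive summary". The same paragraph says the "number of Below Limit of Quantifications will be presented". SAP 11.1 also plans the "number below the limit of quantification (BLQ"), by visit for Baseline and Week 24, on the POE population. It gives no rule for below-limit values in the other statistics, and SAP 14 lists no change here, so the protocol rule stands.
- **Other outputs on this population.** The individual concentration listing (SAP 11.1; Listing 16.2.6.6), and the ADA summaries and listing (Protocol 14.5; SAP 12; Listing 16.2.6.7).

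**The concern.** The population is selected on the result it is meant to describe. A treated subject whose only scheduled post-baseline result is below the LLOQ is removed before the table is built. The planned count cannot reveal that subject, because it is taken on the same population.

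Three outputs are affected. The Week 24 below-limit count loses its meaning. The mean concentration can only err upward. The ADA outputs lose the subjects of most interest: someone whose antibodies had cleared the drug would disappear from ADA incidence, from the treatment-related ADA summary, and from the plot comparing concentrations in ADA-positive and ADA-negative subjects. That last loss matters more than a shift of a few percent in a mean.

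**Working it through.** The documents give no expected concentration, below-limit rate or POE population size, so there is no planned figure to reproduce. I checked the logic first and then the size under stated assumptions.

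**1. Which below-limit values can still be counted?** Read *measurable* as at or above the LLOQ, and list every above/below pattern for one subject.

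| Samples | Patterns | Admitted | Admitted, below limit at scheduled post-baseline visit | Admitted, below limit at baseline |
|---|---|---|---|---|
| Baseline + one scheduled post-baseline | 4 | 2 | 0 | 1 |
| Same + one unscheduled | 8 | 6 | 2 | 3 |

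With scheduled samples only, no admitted subject can be below the limit after baseline. Baseline values below the limit can be counted, and so can a Week 24 value in a subject who also has a measurable unscheduled sample.

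**2. Which rule does what?** The near-zero Week 24 count comes from *measurable* in Protocol 14.2 and SAP 6.3. The below-limit sentence in Protocol 14.5 does not cause it: a value left out of the mean can still be counted. Either rule alone removes the value from the mean, so deleting *measurable* repairs the count but not the mean.

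**3. Effect on the mean.** Let n subjects be assayed and k be below the limit.

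- Against counting them as 0, the reported arithmetic mean is too high by the factor n/(n − k). About 40 randomized 1:1 (Protocol 14.1, SAP 4.3) gives n of about 20: k = 0, 1.00; k = 1, 20/19 = 1.05; k = 2, 20/18 = 1.11.
- SAP 4.1 instead says about 100 randomized, so n of about 50: k = 2 gives 50/48 = 1.04.
- Against 50 ng/mL (LLOQ/2), with measurable levels of m = 500 to 4000 ng/mL (assumed) and n = 20, k = 2: arithmetic mean 500/455 = 1.10 to 4000/3605 = 1.11; geometric mean (m/50)^(2/20) = 10^0.1 = 1.26 to 80^0.1 = 1.55.

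Early exits are sampled at ET, which the SAP 11.1 summary does not list. The Week 24 row may therefore hold fewer than 20 subjects, and each below-limit subject would then weigh more.

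**4. Could it happen without a dosing error?** Subjects who stop study drug for reasons other than relapse are encouraged to keep attending (Protocol 7.1, 8.3). Take a last dose at Week 4 and an assumed level of 500 to 4000 ng/mL at Week 8. Week 24 is 16 weeks later.

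- Half-life 2 weeks (Protocol 5.2.2): 16/2 = 8 half-lives, factor 1/256, leaving about 2 to 16 ng/mL.
- Half-life 12/5 = 2.4 weeks (from 12 weeks being about 5 half-lives, Protocol 7.1): 16/2.4 = 6.67 half-lives, factor about 0.0098, leaving about 5 to 39 ng/mL.

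Both ranges lie below 100 ng/mL. This subject was dosed, yet would appear in neither the exposure nor the ADA tables.

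If each of 20 subjects had an assumed 2%, 5% or 10% chance of a below-limit result, the chance of at least one is 1 − (1 − p)^20 = 33%, 64% or 88%.

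**The case against.** *Measurable* is undefined, and both documents plan a below-limit count, which suggests that such subjects were not meant to be excluded. That is fair as to intent. But if the word adds anything to *evaluable*, a level at or above the LLOQ is its natural sense, and the governing text should not leave it open.

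Excluded subjects also leave a trace. Population membership is tabulated and listed (SAP 9.1; Table 14.1.1.5; Listing 16.2.3.1), and assay results go into the bioanalytical report (Protocol 13.1.2). This stands, but a shortfall in the POE count would not separate a below-limit result from a missing sample, and neither source corrects the planned tables.

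The stakes are limited. POE enters no efficacy analysis and no protocol objective; SAP 5.3 lists concentrations and ADA among the safety endpoints. Protocol 5.2.2 reports low immunogenicity, no neutralizing antibodies, and similar profiles in ADA-positive and ADA-negative subjects, so loss of an antibody-clearing subject is unlikely.

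A reader might infer more than the documents support:

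- *The below-limit count is zero throughout.* It is not; see the baseline and unscheduled cases.
- *The report will show 100% exposure whatever happened.* No percent-exposed output is planned. Dosing problems have their own routes: treatment records (Protocol 9.5.2), deviations (Protocol 15.7.2), and exposure and compliance summaries (SAP 9.6, 9.7).
- *The rule hides placebo kits given to subjects in the active arm.* This is a weak example. Only samples from nemolizumab-treated subjects are assayed, so someone given placebo throughout would not be assayed under either definition.
- *Exposure is overstated.* This holds only if some treated subject is below the limit.

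**Conclusion.** The point holds in a limited form. On the natural reading of *measurable*, a nemolizumab-treated subject below 100 ng/mL at the single scheduled post-baseline sample is removed from the concentration summary, its below-limit count, the concentration listing and the ADA analyses. The Week 24 count is essentially zero by construction.

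The bias in the mean is conditional: none if no sample is below the limit, and about 5% or 11% for 1 or 2 of an assumed 20 subjects, counting them as 0. The geometric mean is more sensitive, but its figures rest on assumed concentrations. The result also assumes one scheduled post-baseline sample per subject. The primary endpoint is untouched. This is a correction worth making because the defect sits in the governing text and also reaches immunogenicity.

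**What to change.** 1. In Protocol 14.2 and SAP 6.3, delete *measurable* and state that an assayed post-baseline result below the LLOQ counts as evaluable. Add the same clarification to the synopsis, whose wording is closer but does not say so.
2. In SAP 11.1, report n and percent below the LLOQ by visit over all assayed nemolizumab-treated subjects.
3. In SAP 11.1, state one rule for below-limit values in summary statistics, replacing the exclusion in Protocol 14.5. LLOQ/2 (50 ng/mL) is one option among several conventions; what matters is that one is fixed in advance.
4. In SAP 12, base the ADA summaries on subjects with an evaluable post-baseline ADA sample, whatever their drug level.

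The cost is wording; no new samples or assays are needed. Protocol 9.3.2 holds back POE and ADA results until after database lock, so the change can be made before anyone on the study team sees them. The downside is that mean concentrations may be slightly lower, and subjects who stopped study drug early but attended Week 24 will contribute low values that do not reflect on-treatment exposure. Flag them or show them separately.

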## 14.6 Interim Analysis

An interim analysis may be conducted for the submission of the regulatory registration of nemolizumab. To maintain blinding, the interim analysis would be carried out by an independent group who are not directly involved in the conduct of the trial.

## 15 STUDY MANAGEMENT

### 15.1 Approval and Consent

#### 15.1.1 Regulatory Guidelines

This study will be conducted in accordance with the accepted version of the Declaration of Helsinki and/or all relevant regulations, as set forth in Parts 50, 56, 312, Subpart D, of Title 21 of the US Code of Federal Regulations (CFR), in compliance with ICH and Good Clinical Practice (GCP) guidelines, and according to the appropriate regulatory requirements in the countries where the study is conducted.

#### 15.1.2 Institutional Review Board/Independent Ethics Committee

Conduct of the study must be approved by an appropriately constituted IEC/IRB. Approval is required for the study protocol, protocol amendments (if applicable), IB, ICFs, recruitment material, and subject information sheets and other subject-facing material.

#### 15.1.3 Informed Consent

For each study subject, written informed consent will be obtained before any protocol-related activities. As part of this procedure, the Principal Investigator (PI) or designee must explain orally and in writing the nature of the study, its purpose, procedures, expected duration, alternative therapy available, and the benefits and risks involved in study participation. The subject should be informed that he/she may withdraw from the study at any time, and the subject will receive all information that is required by local regulations and guidelines for ICH. The PI will provide the Sponsor or its representative with a copy of the IEC-/IRB-approved ICF before the start of the study.

## 15.2 Data Management

The designated CRO will be responsible for activities associated with the data management of this study. This will include, but is not limited to, setting up a relevant database and data transfer mechanisms, along with appropriate validation of data and resolution of queries. All data management activities will be detailed in the data management plan.

Study centers will enter data directly into an EDC system by completing the eCRF via a secure internet connection. Data entered into the eCRF must be verifiable against source documents at the study center. Data to be recorded directly on the eCRF will be identified and the eCRF will be considered the source document. Any changes to the data entered into the EDC system will be recorded in the audit trail.

### **15.3 Source Documents**

Source documents are considered to be all information in original records and certified copies of original records of clinical findings, observations, data, or other activities in a clinical study necessary for the reconstruction and evaluation of the study. The Investigator will provide direct access to source documents and/or source data in the facilitation of trial-related monitoring, audits, review by IECs/IRBs, and regulatory inspections.

The Investigator/institution should maintain adequate and accurate source documents and trial records that include all pertinent observations on each of the study center's trial subjects. Source data should be attributable, legible, contemporaneous, original, accurate, and complete. Changes to source data should be traceable, not obscure the original entry, and be explained if necessary.

Sponsor monitors, auditors, and regulatory inspectors should have direct access to source data.

